6.13. Bioanalytical and Pharmacokinetic/Pharmacodynamic Methods

Blood sample collection for pharmacokinetic analysis is not planned for this study. However, blood samples collected for immunogenicity assessment may be analyzed for ixekizumab serum concentrations to facilitate the interpretation of the immunogenicity data, if needed.

If applicable, a by-patient listing of the ixekizumab serum concentrations will be provided.

6.14. Safety Analyses

Safety will be assessed by summarizing and analyzing AEs, laboratory analyses, vital signs, and Columbia-Suicide Severity Rating (C-SSRS). The duration of treatment exposure will also be summarized.

The primary safety analyses will focus on the comparison of ixekizumab to guselkumab for the Blinded Treatment Periods. For the Post-Treatment Follow-Up Period, safety data will be summarized according to the treatment which patients had received in the Blinded Treatment Periods.

All safety analyses will be conducted on the Safety Population.

Comparisons between treatment groups will be conducted using Fisher's exact test

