### 10.3. Statistical Analyses

#### 10.3.1. General Statistical Considerations

Statistical analysis of this study will be the responsibility of Lilly.

Continuous data will be summarized in terms of the mean, standard deviation, minimum, maximum, median, and number of observations. Categorical data will be summarized as frequency counts and percentages.

Unless otherwise specified, efficacy, and health outcome analyses will be conducted on the ITT population. This set includes all data from all randomized patients according to the treatment the patients were assigned, regardless of whether they received the treatment or not.

The randomization to treatment groups is stratified by site as described in Section 7.2. Study sites with fewer than 5 randomized patients per treatment group will be pooled for statistical analysis purposes. All efficacy and health outcomes analyses will use pooled sites.

All tests of treatment effects will be 2-sided, unless otherwise stated.

The Induction Dosing Period (Period 2) starts at the first injection of study drug at Week 0 (Visit 2) and ends prior to the first injection of study drug at Week 12 or the ETV (between Weeks 0 and 12).

Baseline will be defined as the last available value before the first injection for efficacy, health outcomes, and safety analyses. In most cases, this will be the measure recorded at Week 0 (Visit 2). For efficacy measures, if the patient does not take any injection, the last available value on or prior to the randomization date will be used. Change from baseline will be calculated as the visit value of interest minus the baseline value. For safety analyses using a baseline period, the baseline period is defined as the time from Visit 1 to the date/time of the first injection.

The primary analysis method for treatment comparisons of categorical efficacy, health outcomes variables at specific time points will be made using a Cochran-Mantel-Haenszel (CMH) test stratified by pooled site. Missing data will be imputed using the nonresponder imputation (NRI) method. The 95% confidence interval (CI) associated with the treatment response rate, and treatment difference will be provided. Secondary analysis will be conducted using a Fisher's exact test.

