### 10.3.4. Safety Analyses

Safety will be assessed by summarizing and analyzing AEs including adjudicated cerebro-cardiovascular events, laboratory analytes including neutrophil counts, and C-SSRS. The duration of treatment exposure will also be summarized.

The safety analyses will focus on comparison of ixekizumab to guselkumab for the Induction Dosing Period (Period 2). Safety data will also be separately summarized for the combined Induction Dosing Period (Period 2) and Extension Period (Period 3), as well as Post-Treatment Follow-Up (Period 4). All safety analyses will be conducted on the Safety Population.

The categorical safety measures will be summarized with incidence rates. The mean change of the continuous safety measures will be summarized by visits.

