#### 10.3.4.1. Adverse Events

Adverse events are classified based upon the Medical Dictionary for Regulatory Activities (MedDRA). A TEAE is defined as an event that first occurred or worsened in severity after

baseline and on or prior to the date of the last visit within the treatment period. Both the date/time of the event onset and the date/time of the first study drug injection are considered when determining TEAEs. Treatment-emergent adverse events will be assigned to the treatment period in which they first occurred or worsened. A follow-up emergent AE (FEAE) is defined as an event that first occurred or worsened in severity after the date of Week 24 or the ETV. For events that are gender specific, the denominator and computation of the percentage will include only patients from the given gender.

An overall summary of AEs will be provided for each of the treatment periods, including the number and percentage of patients who experienced TEAEs, TEAEs by maximum severity, deaths, SAEs, TEAEs related to study drug, discontinuations from the treatment due to an AE, and treatment-emergent AESIs. Treatment-emergent AEs (all, by maximum severity, and TEAEs possibly related to study drug by the investigator), SAEs including deaths, and AEs that lead to treatment discontinuation will be summarized and analyzed by MedDRA System Organ Class, and Preferred Term.

In addition to general safety parameters, safety information on specific topics of AESIs will also be presented. Potential AESIs will be identified by a standardized MedDRA query or a Lilly defined MedDRA preferred term listing.

Follow-up emergent adverse events, SAEs including deaths, and AEs that lead to study discontinuation will be summarized for Post-Treatment Follow-Up Period (Period 4).

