5.1. Summary of Study Design

Study IIF-MC-RHCR (RHCR) is a Phase 3b/4, multicenter, randomized, double-blind, parallel-group study evaluating the efficacy and safety of ixekizumab versus guselkumab in patients with moderate-to-severe plaque psoriasis during a 24-week treatment period.

The following treatment groups will be assessed in this study:

- Ixekizumab: 80-mg subcutaneous (SC) injection. At Week 0, a 160-mg starting dose (two 80-mg injections), followed by 80 mg every 2 weeks (Q2W) from Weeks 2 through 12, and then followed by 80 mg every 4 weeks (Q4W), thereafter (i.e., at Weeks 16 and 20).
- Guselkumab: 100-mg SC injection. At Weeks 0 and 4, a 100 mg injection, followed by 100 mg every 8 weeks (Q8W), thereafter (i.e., at Weeks 12 and 20).

[figure not shown]
The study will consist of 4 periods:

- **Period 1: Screening Period** (Visits 1) will assess patient eligibility, occurring approximately 5 to 28 days prior to Period 2 (baseline; Week 0 [Visit 2]).
- **Period 2: Induction Dosing Period** will occur from Week 0 (baseline; Visit 2) to Week 12 (Visit 9), inclusive.
- **Period 3: Extension Period** will occur from Week 12 (Visit 9) up to Week 24 (Visit 12), inclusive.
- **Period 4: Post-Treatment Follow-Up Period** occurring from last treatment period visit (Week 24) or Early Termination Visit (ETV), for a minimum of 12 weeks following that visit.

In the remainder of this statistical analysis plan (SAP), if Period 2 (Induction Dosing Period) and Period 3 (Extension Period) are combined for analysis, they will be referred to as **Blinded Treatment Periods**.

Figure RHCR.5.1 illustrates the study design.

In addition to procedures specified in the protocol, a subset of patients will participate in a Photograph and/or Skin Biopsy addendum/addenda. Sites will be selected by the Sponsor, and some patients at those sites will participate in the addendum/addenda; separate informed consent(s) will be obtained.

Abbreviations: d = day(s); GUS = guselkumab; IXE = ixekizumab; LV = last visit; Q2W = every 2 weeks; Q4W = every 4 weeks; Q8W = every 8 weeks; R = randomization; V = study visit; W = study week.

Figure RHCR.5.1. Illustration of study design for Clinical Protocol I1F-MC-RHCR.

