6.18. Interim Analyses

The study will have one interim database lock once all patients complete Visit 9 (Week 12) or discontinue in the Induction Dosing Period. The interim analysis will include all data collected by the cutoff date, including the data from the Extension Period and the Post Treatment Follow-Up Period. The interim database lock at Week 12 will be considered the primary database lock because all primary and major secondary objectives, except for PASI 100 at Week 24, will be assessed at this time.

Prior to the Week 12 database lock, all members of the study team will be blinded to the treatment allocations. At the time of the Week 12 database lock, study team members that have direct access to study sites and data collection will remain blinded to the treatment allocations until all patients have completed the study (or discontinued on or prior to Week 24) and final database lock has occurred. Site staff, clinical monitors, and patients will remain blinded to the patient treatment allocation until the final Clinical Study Report (CSR) has been approved.

A final database lock will occur after the Post-Treatment Follow-Up Period is completed.

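### The SAP moves the main between-arm safety comparison from Period 2 to the combined 24 weeks without explanation, and specifies no Period 2 comparison

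*SAP*

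**What the plan says.** Protocol 10.3.4 sets the focus: "The safety analyses will focus on comparison of ixekizumab to guselkumab for the Induction Dosing Period (Period 2"). It then gives the combined periods a secondary place: "Safety data will also be separately summarized for the combined Induction Dosing Period (Period 2) and Extension Period (Period 3"). Protocol 10.3.4.1 assigns each TEAE to the treatment period in which it arose or worsened, and adds: "An overall summary of AEs will be provided for each of the treatment periods". Protocol 10.3.1 defines when Period 2 finishes for analysis: it "ends prior to the first injection of study drug at Week 12 or the ETV (between Weeks 0 and 12").

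SAP 6.14 sets a different focus: "The primary safety analyses will focus on the comparison of ixekizumab to guselkumab for the Blinded Treatment Periods". SAP 5.1 explains the term: "if Period 2 (Induction Dosing Period) and Period 3 (Extension Period) are combined for analysis, they will be referred to as" the Blinded Treatment Periods. For the Week 12 lock, SAP 6.18 says: "The interim analysis will include all data collected by the cutoff date, including the data from the Extension Period". Both SAP 6.18 and protocol 10.3.7 treat that lock as the primary one.

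**The concern.** The protocol promises a between-arm safety comparison over the same 12 weeks as the primary efficacy endpoint. A programmer following the SAP would not produce it. If it were requested after the Week 12 unblinding, it would be a post hoc analysis, although the protocol had planned it.

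The two windows answer different questions. Period 2 describes safety during induction dosing, next to PASI 100 at Week 12. The combined periods describe 24 weeks, over which the ixekizumab interval changes from two to four weeks. Readers of the Week 12 results would want the first, and the protocol told them to expect it.

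**Working it through.** No stated sample size, power or alpha depends on this point, so there is no plan figure to reproduce. The check is a comparison of text, followed by one illustration with assumed rates.

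**1. The two documents side by side**

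| Item | Protocol | SAP |
|---|---|---|
| Main between-arm safety window | Period 2 (10.3.4) | Periods 2 and 3 combined (6.14, 5.1) |
| Combined periods | Separate additional summary (10.3.4) | Primary comparison (6.14) |
| AE overview | One for each treatment period (10.3.4.1) | Combined periods (6.14.2) |
| Windows listed for comparison | Not tabulated | Combined periods: compared; follow-up: not compared (Table RHCR.6.2) |

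The SAP sets its between-arm analyses for the combined periods in 6.14.2 (TEAEs), 6.14.3 (SAEs and AEs leading to discontinuation), 6.14.3.1 with Table RHCR.6.8 (AESIs) and 6.14.5 (laboratory abnormalities).

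**2. Does other SAP text restore a Period 2 comparison?** SAP 6.14.2 assigns TEAEs to a study period, 6.14.5 summarises laboratory abnormalities by study period, and 6.14.5.1 takes minima within a study period. Table RHCR.6.2 lists only two study periods, the combined one and follow-up, and 6.14.5 attaches its Fisher test to the combined one. By-visit laboratory box plots (6.14.5) and weight summaries (6.14.6) do show Week 12, but they are descriptive and do not cover AEs.

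**3. Does the Week 12 lock supply it?** No. Data are not cut at Week 12. At the lock, a patient's Extension follow-up lies between 0 and 24 − 12 = 12 weeks, depending on enrolment date. The documents do not give the enrolment duration, so the spread within that range is unknown.

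**4. Laboratory change.** SAP 6.14.5 tests change from baseline to last observation over the combined periods. The Schedule of Activities places post-baseline chemistry at Weeks 12 and 24, and hematology at Weeks 4, 12, 16 and 24. For a completer at final lock, the last scheduled value is Week 24. At the Week 12 lock, it is whichever visit the patient has reached. Neither is a test of Week 12 change. Protocol 7.3.1 has assessments done before the Week 12 dose, so the Week 12 sample belongs to Period 2 under the 10.3.1 boundary.

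**5. Are the two comparisons interchangeable?** Assumptions, none from the documents: background AE risk g in each 12-week period in both arms; a 5-point excess on ixekizumab during induction; all 480 planned patients per arm in the safety population. The test is a two-sided Fisher test at 0.05. (The same exact calculation gives 98.6% and 95.5% for the plan's two superiority powers, stated as 98% and 95%.)

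- Period 2: g + 0.05 versus g.
- 24 weeks, excess confined to induction: 1 − (1 − g − 0.05)(1 − g) versus 1 − (1 − g)².
- 24 weeks, same excess in both periods: 1 − (1 − g − 0.05)² versus 1 − (1 − g)².

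| g | Period 2: rates, power | 24 weeks, induction only: rates, power | 24 weeks, persisting: rates, power |
|---|---|---|---|
| 5% | 10% v 5%, 81% | 14.5% v 9.75%, 58% | 19% v 9.75%, 98% |
| 10% | 15% v 10%, 62% | 23.5% v 19%, 37% | 27.75% v 19%, 88% |
| 20% | 25% v 20%, 43% | 40% v 36%, 23% | 43.75% v 36%, 67% |

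The combined window loses sensitivity if the excess stops at Week 12 and gains it if the excess continues. Neither comparison can stand in for the other.

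**The case against.** The best defence is that this is a 24-week trial of two complete regimens, each described in protocol 5.5 as approved dosing. Safety over the full regimen is a sensible target, and the protocol plans a combined summary. No safety hypothesis or error rate depends on the window. Protocol 10.3.1 also lets analysis methods change without an amendment unless a principal feature is altered, provided that the change and its justification appear in the CSR. All of this stands as a reason to keep the combined comparison. It does not explain why the Period 2 comparison disappeared, and the SAP gives no justification.

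Several stronger readings are tempting but unsupported:

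- *The Period 2 analysis is ruled out.* The SAP does not specify it; it does not forbid it.
- *All SAP safety tables are combined-period only.* Follow-up tables and by-visit displays exist. The gap is in Period 2 between-arm comparisons.
- *Unequal Extension follow-up biases the Week 12 comparison.* Randomisation is concurrent, 1:1 and stratified by site, so enrolment date is balanced in expectation, and SAP 6.14.1 reports patient-years by arm. What is lost is a defined exposure window.
- *Pooling dilutes early events by a known amount.* Every induction event is still counted over 24 weeks. Any loss of contrast depends on rates that the documents do not give, and it can reverse.
- *The split of injections around Week 12 measures the harm.* Seven of ten ixekizumab injections precede the Week 12 dose, but footnote b of Table RHCR.7.2 counts Week 12 with the two-weekly doses, giving eight and two. Neither split says anything about event rates.

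**Conclusion.** The conflict is real and undocumented. Following the SAP omits a between-arm comparison that protocol 10.3.4 makes the focus, for five classes of safety outcome, together with any between-arm test of laboratory change at Week 12. At the primary lock, the combined-period incidences would have no fixed exposure window and would not align with the primary efficacy result.

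This is a specification gap, not a demonstrated bias. It should be corrected, but it does not threaten the primary efficacy conclusion. The finding rests on reading Table RHCR.6.2 as the full list of windows for comparison, which the later safety sections bear out. The power figures show only that the two windows differ; they are not an estimate of loss in this trial.

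**What to change.** In SAP 6.14 and Table RHCR.6.2, add Period 2 between-arm tables for TEAEs, SAEs, AEs leading to discontinuation, AESIs and laboratory abnormalities, as the focus comparison stated in protocol 10.3.4. Include laboratory change to the end of Period 2. Define the window as in protocol 10.3.1, from first injection to just before the Week 12 injection. This boundary needs stating because SAP 5.1 places the Week 12 visit in both periods. Keep the combined 24-week comparison alongside.

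If the sponsor wants the combined periods to be primary, it should still produce the Period 2 tables, and should document and justify the change under protocol 10.3.1.

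The cost is SAP wording and one more run of existing table programs with a date cut. No new data are needed. The change should be made before the Week 12 unblinding, so that the comparison remains prespecified.

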6.14.1. Extent of Exposure

Duration of exposure to study drug will be summarized by treatment for safety population during the Blinded Treatment Periods using descriptive statistics.

The duration of exposure to treatment during the Blinded Treatment Periods will be calculated as:

Duration of exposure (days) =

Date of last visit (scheduled or unscheduled) in the Blinded Treatment Periods – Date of first injection + 1

For patients who discontinued treatment due to lost to follow-up, duration of exposure will be calculated with date of second to the last visit (scheduled or unscheduled) in treatment period will be used in replacement of date of last visit (scheduled or unscheduled) in treatment period.

The number and percentage of patients in each of the following categories will be included in the summaries:

- >0, ≥7 days, ≥14 days, ≥30 days, ≥60 days, ≥90 days, ≥120 days, and ≥168 days.
Note that patients may be included in more than 1 category.
- >0 to <7 days, ≥7 to <14 days, ≥14 to <30 days, ≥30 to <60 days, ≥60 days to <90 days, ≥90 to <120 days, ≥120 to <168 days, and ≥168.

The summaries will also include the following information:

- Total exposure in patient years, calculated as:

Total exposure in patient years =

Sum of duration of exposures with the defined treatment period (for all patients in treatment group) / 365.25

- Number of active injections taken is derived using the response to the question “Was dose administered?” on the Exposure eCRF page and the actual dose description from IWRS study drug dispense dataset.
- Total dose (in mg) is calculated as:

Total Dose = Sum of dose for each active injection taken during the defined treatment period

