**Table RHCR.7.1. Treatment Regimens**

Randomized Treatment Group	Starting Dose W0	Dose W2-W12	Dose a W16-W20
Ixekizumab	Ixekizumab 80 mg 2xSC (total of 160 mg)	Ixekizumab 80 mg SC at W2, 4, 6, 8, 10, and 12	Ixekizumab 80 mg SC at W16 and 20
Guselkumab	Guselkumab 100 mg SC; Placebo	Guselkumab 100 mg SC at W4 and 12; Placebo at W2, 6, 8, and 10	Guselkumab 100 mg SC at W20; Placebo at W16

Abbreviations: SC = subcutaneous injection; W = Week.

a No dose is given at W14; therefore, W14 is not included in this table.

The investigator or his/her designee is responsible for the following:

- explaining the correct use of the investigational agent(s) to site personnel/legal representative
- verifying that instructions are followed properly
- maintaining accurate records of study drug dispensing and collection
- returning all unused medication to Lilly or its designee at the end of the study

Note: In some cases, sites may destroy clinical trial material if during the investigator site selection, the evaluator has verified and documented that the site has appropriate facilities and written procedures for disposing of clinical trial materials.

Designated Unblinded Site Personnel will be responsible for the handling, dispensing, and administering of all study drugs (ixekizumab, guselkumab, and placebo). Additional details regarding Unblinded Site Personnel responsibilities are provided in the Unblinded Site Personnel Dispensing and Dosing Instructions. Unblinded Site Personnel will not be involved in patient screening, enrollment, and any assessment of efficacy or safety. It is critical that the blind is maintained throughout the study (24 weeks).

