#### 7.3.1. Selection and Timing of Doses

Patients will be assigned to treatment and will receive their assigned treatment as outlined in Sections 7.1.1.

Study drug should be administered on the same day of the week, at approximately the same time each day, as much as possible. The actual time of all dose administrations will be recorded in the subject's case report form (CRF). For injections not administered on the scheduled day of the week from Weeks 0 to 12, the missed dose should be administered within 3 days of the scheduled day; after Week 12, the missed dose should be administered within 5 days of the scheduled day. Dates of subsequent study visits should not be modified according to the delay of the injection of the missed scheduled dose. The doses at Weeks 0 to 12 should not be administered until after all assessments per the Schedule of Activities (Section 2) are completed.

Throughout their participation in the study, site personnel will record information in a Study Drug Administration Log, including the date, time, and anatomical location of administration of study drug (for treatment compliance), syringe number, who administered the study drug, and the reason if study drug was not administered or not fully administered.

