### **8.3. Lost to Follow-Up**

A patient will be considered lost to follow-up if he or she repeatedly fails to return for scheduled visits and is unable to be contacted by the study site. Site personnel are expected to make diligent attempts to contact patients or their families/relatives who fail to return for a scheduled visit or were otherwise unable to be followed up by the site.

Lilly personnel will not be involved in any attempts to collect vital status information.

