screen	The act of determining if an individual meets minimum requirements to become part of a pool of potential candidates for participation in a clinical study.
study drug	A pharmaceutical form of an active ingredient or placebo being tested or used as a reference in a clinical trial, including products already on the market when used or assembled (formulated or packaged) in a way different from the authorized form, or marketed products used for an unauthorized indication, or marketed products used to gain further information about the authorized form.
SUSARs	suspected unexpected serious adverse reactions
TB	tuberculosis

TBL	total bilirubin level
TEAE	Treatment-emergent adverse event: An untoward medical occurrence that emerges during a defined treatment period, having been absent pretreatment, or worsens relative to the pretreatment state, and does not necessarily have to have a causal relationship with this treatment.
Th	T helper
TNF	tumor necrosis factor
TNFi	TNF inhibitor
TPO	third-party organization
ULN	upper limit of normal
USPI	United States Package Insert
VAS	visual analog scale
WBC	white blood cell

---

---

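### For patients lost to follow-up, SAP 6.14.1 ends exposure at the second-to-last visit; on its plain wording this understates exposure by 7 to 28 days and leaves Week 0-only patients with no value

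*SAP*

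**What the plan says.** SAP 6.14.1 gives a general formula for duration of exposure: "Date of last visit (scheduled or unscheduled) in the Blinded Treatment Periods – Date of first injection + 1". It then makes an exception for patients who discontinue because they are lost to follow-up, for whom "duration of exposure will be calculated with date of second to the last visit (scheduled or unscheduled) in treatment period" replaces the last visit. No reason is given. There is no floor at the date of the last dose, and no provision for a patient with only one treatment-period visit.

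Protocol 8.3 treats a patient as lost when he or she "repeatedly fails to return for scheduled visits and is unable to be contacted by the study site".

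Protocol Table RHCR.7.1 sets the injection visits. After the Week 0 starting dose, the ixekizumab arm has "Ixekizumab 80 mg SC at W2, 4, 6, 8, 10, and 12" and then "Ixekizumab 80 mg SC at W16 and 20". The guselkumab arm is injected at the same visits, with placebo filling the gaps: "Guselkumab 100 mg SC at W4 and 12; Placebo at W2, 6, 8, and 10", then placebo at Week 16 and active drug at Week 20. Protocol Appendix 1 counts placebo as study drug ("A pharmaceutical form of an active ingredient or placebo being tested"). Protocol 7.3.1 places the dose at the visit, after the assessments: "The doses at Weeks 0 to 12 should not be administered until after all assessments per the Schedule of Activities".

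**The concern.** For someone who simply stops coming, the last visit on record should be one the patient attended, and it is nearly always a visit at which study drug was injected. Stepping back one visit then closes exposure before a dose that was given. If Week 0 is the only treatment-period visit, there is no earlier visit to step back to. The patient is in the safety population but fits no duration category, not even the one for more than 0 days.

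The exception also differs from the dates used elsewhere in the SAP. For time-to-event analyses, Sections 6.1.3 and 6.5 censor patients who lack a completion date at the later of last dose and last attended visit. Section 6.14.2 runs the treatment-emergent window to the last visit, so an event between the last two visits could be counted as treatment-emergent after that patient's exposure had closed.

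At stake are the duration, duration-band and patient-year figures in the exposure table.

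**Working it through.** The SAP states no exposure figure under this rule, so there is none to reproduce. The check applies the rule to each possible last attended visit.

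**Inputs.** Nominal visit days from the Schedule of Activities: Week 0 = 0, Week 1 = 7, Week 2 = 14, Week 4 = 28, Week 6 = 42, Week 8 = 56, Week 10 = 70, Week 12 = 84, Week 16 = 112, Week 20 = 140. Injections fall at 9 of these 10 visits (all but Week 1).

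**Formulas.** Exposure to last visit = day of last visit + 1. Exposure under the rule = day of previous visit + 1. Example for Week 16: 112 + 1 = 113 against 84 + 1 = 85, a shortfall of 28.

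| Last attended visit | To last visit (days) | Under the rule (days) | Shortfall (days) | Last injection on day | SAP duration band under the rule |
|---|---|---|---|---|---|
| Week 0 | 1 | undefined | – | 1 | none |
| Week 1 | 8 | 1 | 7 | 1 | lower |
| Week 2 | 15 | 8 | 7 | 15 | lower |
| Week 4 | 29 | 15 | 14 | 29 | same |
| Week 6 | 43 | 29 | 14 | 43 | lower |
| Week 8 | 57 | 43 | 14 | 57 | same |
| Week 10 | 71 | 57 | 14 | 71 | lower |
| Week 12 | 85 | 71 | 14 | 85 | same |
| Week 16 | 113 | 85 | 28 | 113 | lower |
| Week 20 | 141 | 113 | 28 | 141 | lower |

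For last visits at Weeks 2 to 20, exposure closes before the last injection. For Week 1 it closes on the day of the last injection, so 7 days of follow-up are lost but no dose is cut off. For Week 0, falling back on screening (5 to 28 days earlier) would give −5 + 1 = −4 to −28 + 1 = −27 days, and screening is not a treatment-period visit anyway.

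Visit windows move these figures by some days. An intervening unscheduled visit would shrink a shortfall, and a missed visit just before the last one would widen it.

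**Comparison with dose in the same table.** Active injections and total dose come from the Exposure eCRF and IWRS data, so they are not cut. An ixekizumab patient lost after Week 20 would show 2 + 6 + 2 = 10 injections and 10 × 80 = 800 mg, with 113 days of exposure and the tenth injection on day 141. In the guselkumab arm, active doses fall at Weeks 0, 4, 12 and 20, so exposure closes before the last active dose only for last visits at Weeks 4, 12 and 20.

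**Size.** Protocol 5.2 anticipates 5% dropout: 0.05 × 960 = 48 patients. The lost-to-follow-up share is not given.
- If all complete, total exposure is 960 × 169 / 365.25 = 444.2 patient-years.
- Extreme case, all 48 lost with the 28-day shortfall: 48 × 28 / 365.25 = 3.7 patient-years, or 3.7 / 444.2 = 0.8%. Counting only the 912 completers in the denominator: 1,344 / (912 × 169) = 1,344 / 154,128 = 0.9%.
- Assumed 1% lost (9.6 patients): at most 9.6 × 28 / 365.25 = 0.7 patient-years, or 0.2%.

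**The case against.** The strongest reply is that visit need not mean attended visit here. SAP 6.1.3 and 6.5 write last attended visit; 6.14.1 writes only last visit. Protocol 5.1.2 and 5.1.3 send patients who stop study drug for any reason to an early termination visit. If the database enters a dated termination record for a lost patient, the second-to-last visit is the last one attended, a Week 0-only patient gets 1 day, and the anomalies disappear. This may be what the authors intended. The documents do not exclude it, but nothing states it, and the Protocol 8.3 definition gives no reason to expect an attended termination visit. What stands is that the finding is conditional on the plain wording. The proposed fix gives the same answer as this alternative reading.

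A reader might infer that safety rates are distorted because patient-years are their denominator. The documents do not support that. SAP 6.14 only summarises exposure, SAP 6.14.2 reports AEs as numbers and percentages of patients, and the comparisons use Fisher's exact test. The one exposure-scaled AE measure, injection-site reactions per 100 active injections, uses injection counts, which the rule leaves alone.

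A reader might also infer that the exposure table contradicts its own dose figures for every lost patient. Because only active injections are counted, this fails for guselkumab patients whose last visit was a placebo visit (Weeks 2, 6, 8, 10 and 16).

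**Conclusion.** The point holds as a minor defect in a stated rule. It rests on reading last visit as an attended visit and on nominal visit days with no intervening unscheduled visits. On that basis every patient lost from Week 1 onward has exposure understated by 7, 14 or 28 days. Six of the ten possible last visits (Weeks 1, 2, 6, 10, 16 and 20) put the patient in a lower duration band, and Week 0 gives no value.

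The consequence is small: below 1% of patient-years in the extreme case and about 0.2% at most with an assumed 1% lost. It reaches only a descriptive summary. Injection counts, total dose, AE percentages, tests and efficacy results do not change. It is worth correcting because the individual values are wrong on the plain wording and the remedy is simple, not because any trial conclusion depends on it.

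**What to change.** Replace the second-to-last-visit sentence in SAP 6.14.1. For patients lost to follow-up, define duration as the later of the last dose date and the last attended visit date in the Blinded Treatment Periods, minus the date of first injection, plus 1. State that administrative disposition dates are not visits.

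This uses the dates already in SAP 6.5, gives a Week 0-only patient 1 day, and keeps exposure from closing before a dose that was given. The cost is about one sentence in the SAP and a small programming change; no new data are needed.
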